Expected results: It is expected that this randomized controlled study will show the effects on quality adjusted life years, cost-efficiency, and cost-utility of two different primary assessors for patients with suspected knee osteoarthritis consulting primary care. The results could clarify which profession that is most appropriate to be the primary assessor for patients with suspected knee osteoarthritis in primary care.

.....

Detailed Description

Problem statements

What is the difference in cost efficiency between a healthcare process with a physiotherapist as primary assessor and a physician as primary assessor for patients with suspected KOA?

Which effect does a clinical pathway with a physiotherapist as primary assessor for patients with suspected knee osteoarthritis have on quality adjusted life years compared with a physician as primary assessor?

What are the differences in costs between the two healthcare processes initiated by either a physiotherapist or a physician set against the differences in effects?

Patient recruitment

Some data has already been collected for another clinical trial (ID: NCT03715764), which will be used in this study too. The patient recruitment is finished, while data collection regarding cost variables has not started yet.

Patients were recruited from primary care centers and rehabilitation centers in southwestern Sweden.

Screening procedure

Nurses and administration personnel at the recruitment units got information about the study and the screening protocol from the data collector and project leader. Each recruiting unit had a contact person that were responsible for the protocols and to contact the data collector when an eligible patient was found. It was regular contact between the project leader and the contact persons at the recruiting units. All screening protocols were sent to the data collector. All participants got orally and written information about the study from the data collector, and patients provided written informed consent.

Randomization

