A computer-generated list of random numbers was used, where participants were randomly assigned to being assessed, diagnosed and treated either by a physiotherapist or a physician first. The project coordinator managed the sequence generation, allocation concealment, enrolment and assignments of participants and kept the concealed randomization scheme and sequentially numbered, sealed envelopes in a locked cupboard (in the same building where the enrolment was), only available for the project coordinator. The project coordinator revealed the allocation to the participant shortly after the baseline measurement and to the health care providers. Data collector, data analyst and statistician were blinded of allocation until completion of data collection for the primary outcome measures at the 12 months follow up for the last recruited patient. Group allocation was revealed when analyzing data for the other clinical trial (ID: NCT03715764).

The project coordinator was not involved in the screening procedure nor the data collection and was **not** included among the healthcare providers in the study. The blinded data collector and analyst, whom is a physiotherapist, were not involved in assessing, diagnosing and treating patients with knee osteoarthritis while the first study (ID: NCT03715764) was conducted.

Data collection

Demographic data and measurements of **health-related quality of life** (HrQoL) has already been collected for another clinical trial (ID: NCT03715764). These data will also be used for the cost-efficiency analysis. Demographic data were collected at baseline. Measurements of HrQoL were measured with EuroQol 5 dimensions 3 levels (EQ5D-3L) and collected at baseline (before randomization), 3-, 6- and 12 months follow ups.

New data collection will be made for cost variables. Data regarding costs for the healthcare processes will be extracted from patient journals. The costs for visits to **physiotherapist**, physician or other healthcare provider will be collected from the healthcare organization. The drug prices will be collected from the Swedish Association of Local Authorities and Regions for the time period the drugs were prescribed. Production loss due to sick-leave and health care visits will be valued according to mean gross salary (including taxes and social fees).

Calculating total costs (number of contacts per patient * costs) for:

- Physiotherapy contacts in primary care
- Physician contacts in primary care

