- Referrals to x-ray
- Referrals to other healthcare givers
- Drug prescriptions
- Sick-leave days

Data management

All data will be coded and managed according to the General Data Protection Regulation. All data will be confidential and only authorized will have access to the patient registry. No individual information can be identified since the results will be presented at group level. Data will be saved for at least 10 years to enable audit.

Sample size

A sample size of 50 patients per group will be necessary to detect a minimal clinical improvement of 0.121(SD 0.2) on the EQ5D-3L-index, given an anticipated dropout rate of 14%. The sample size calculation was calculated with a two-sided 5% significance level and a power of 80%.

Statistical analysis plan

Data will be analyzed descriptively and presented as numbers and percent, mean and standard deviation or median and 25th to 75th percentiles. Statistical analysis will be made in SPSS Windows and the analysis will be applied with intention-to-treat (ITT).

The economic evaluation will be developed together with a health economist. The method will be a cost-effectiveness analysis alongside the clinical trial comparing costs and effects for the two alternatives based on collected data from the trial. The EQ5D-3L measurements will be used for analyzing quality adjusted life years. The result will be presented as an incremental cost-effectiveness ratio (ICER) and a non-parametric bootstrapping will be conducted to demonstrate the uncertainties surrounding the ICER.

Study Design

Study Type: Interventional (Clinical Trial)

Actual Enrollment: 69 participants

Allocation: Randomized

Intervention Model: Parallel Assignment

Participants with suspected knee osteoarthritis **were** either randomized to a physiotherapist or a physician as primary assessor for assessment and treatment. After the first assessment that the patients **were** assigned to, the patients **could** choose to seek the other health care provider if they **wanted** to. This study focuses on analyzing cost efficiency of the health care processes for patients with suspected knee osteoarthritis in primary care.

Masking: Single (Outcomes Assessor)

Primary Purpose: Treatment

Arms and Interventions

Physiotherapist as primary assessor - Intervention

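### Does the single-masked label overstate the protection of the cost outcomes?

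*Combined protocol and SAP*

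**What the plan says.** The Study Design section lists the design as short entries, one of which is "Masking: Single (Outcomes Assessor". It names no outcome and no period.

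The Randomization section gives the detail. "Data collector, data analyst and statistician were blinded of allocation until completion of data collection for the primary outcome measures", at the 12-month follow-up of the last patient recruited. It then adds: "Group allocation was revealed when analyzing data for the other clinical trial". It also says that participants and care providers were told the allocation shortly after the baseline measurement.

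On timing, the Patient recruitment section says: "The patient recruitment is finished, while data collection regarding cost variables has not started yet". The Data collection section says that the EQ-5D-3L came from the earlier trial and was "collected at baseline (before randomization), 3-, 6- and 12 months follow ups". For costs it says "New data collection will be made for cost variables" and "Data regarding costs for the healthcare processes will be extracted from patient journals".

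Secondary Outcome Measures defines six cost outcomes, A to F: physiotherapy contacts, physician contacts, sick leave, drug prescriptions, x-ray referrals and other referrals. Each is a number of recorded items multiplied by a cost, from baseline to one year. No section says who reads the journals or whether that person knows the allocation.

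**The concern.** Read in date order, the blind ended, allocation was revealed, and only then was cost extraction to begin. The only data newly collected under this protocol therefore fall outside the documented blind, while the label states no such limit.

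Costs form the numerator of the incremental cost-effectiveness ratio, and the study describes itself as an analysis of cost efficiency. If an extractor who knew the allocation had to decide which items count, those decisions could differ between arms and shift the cost difference. The documents leave some room for judgement. The cost list under Data collection mentions x-ray and other referrals without a body part, whereas outcomes E and F limit them to the knee. Outcomes A to D state no knee limit in either place. A reader who took the label at face value would not look for this risk.

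**Working it through.** The concern contains no figure to reproduce, so the check sets the sections side by side.

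**1. Is the chronology right?** Yes. The blind ran to the end of primary-outcome collection (Randomization). The primary outcome is the EQ-5D-3L, last collected at 12 months (Primary Outcome Measures, Data collection). If the Randomization text means the earlier trial's primary outcomes, the end point is still the 12-month follow-up. Cost collection had not begun (Patient recruitment). No masked extractor is described, and none is excluded.

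**2. Does any section claim that the cost data are masked?** No. The label is one field in a run that also covers allocation, intervention model and purpose. The Randomization section says which staff were blinded, until when, and that allocation was later revealed. The two fit together as a short entry and its detail. The limit of the blind is disclosed in the same document.

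**3. What could knowledge of allocation still alter?** The cost window is baseline to one year after baseline. The blind lasted until the last patient's 12-month follow-up. By the reveal, the window had essentially closed for every patient, and the events in it lay in routine journals. The reveal to study staff could not change what had been recorded, only how it was read out. Prices come from outside the extraction: the healthcare organization for visits, a national body for drugs, and mean gross salary for production loss.

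**4. How much judgement does the extraction need?**

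| Outcome | Cost list (Data collection) | Definition (Secondary Outcome Measures) | Reading |
|---|---|---|---|
| A, B | contacts in primary care | visits in the journal, setting not repeated | compatible; the study concerns primary care |
| C, D | sick-leave days, prescriptions | the same items, no knee limit | compatible; knee-related or all is not stated |
| E, F | referrals, no body part | referrals for the knee | category name, then narrower definition |

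For E and F the definition settles the scope, and whether an x-ray referral concerns the knee needs little discretion. The open question is whether A to D count all registered items or only knee-related ones. The definitions, taken literally, count registered items. No section suggests a rule that differs by arm.

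**5. Would masking the extractor be feasible?** Hardly. Outcomes A and B are counts of visits to the two professions being compared, so the record read for the outcome shows who saw the patient and when.

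**6. Is the EQ-5D so much better protected?** All four EQ-5D time points precede the end of the blind, and none of the six cost outcomes was extracted before it. That contrast overstates the difference. The EQ-5D is self-rated, and participants knew their allocation at three of the four time points (3, 6 and 12 months). The documented blind covers the staff handling and analysing the questionnaires, not the raters.

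**The case for a change.** The strongest case for a change is that labels are often read alone and that this one covers a study whose main result depends on cost data with no documented masking. Since masking is barely practicable here, a written inclusion rule is the main safeguard available, and it would cost a few sentences.

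The scope of the costs is also not fully settled. The Data collection section prices visits to other providers, whereas outcome F counts referrals. It values production loss from healthcare visits, which appears neither in the cost list nor in A to F. Arms and Interventions names prescriptions, x-ray, other referrals and sick leave only under the physician arm, so a loose rule might not affect the arms equally.

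Much of this stands as description. The label is broader than the documented blind, the extractor is not identified, and the scope of some cost items could be stated more fully. However, the scope questions exist whether or not the extractor is masked, and they do not show that masking was misreported. Part of the rule is already written: the one-year window for all six outcomes, visits registered in the journal for A and B, and the knee limit for E and F. The objection does not show that applying the plan as written, in the same way to both arms, gives a wrong cost difference.

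**Conclusion.** No change to the plan follows. The label is a summary entry whose limit is disclosed under Randomization. Rewording it would alter no estimate. Naming the extractor, and saying whether A to D count knee-related or all registered items, would fill in detail that a competent analyst and the health economist would settle in the ordinary course and report with the results.

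The size of any effect cannot be estimated, because the documents give no contact counts and no unit prices. The room for bias looks small for counts of recorded events multiplied by outside prices.

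This conclusion assumes that one inclusion rule is applied in both arms, which nothing in the documents contradicts, and that the results are not reported as if cost extraction had been masked. Evidence of arm-dependent extraction, or a report claiming masked cost data, would reopen the point.

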STUDY PROTOCOL WITH STATISTICAL ANALYSIS PLAN

Official title:

A Cost-efficiency Analysis of Primary Assessors for Patients With Knee Pain in Primary Care

NCT number: NCT03822533

The Regional Ethical Review Board in Gothenburg approved the study 2013-03-15, reference numbers: 979–12, T674–13, T497–14, T791–15 and 2020-00432.

Document date: Protocol published and released on clinicaltrial.gov 2019-01-30. Minor spelling and grammar changes made 2022-08-08, which are highlighted in yellow.

Sponsors: Region Vastra Gotaland, Närhälsan, Sweden

Principal Investigator: [name]

Närhälsan Research and development center Södra Älvborg

Contact person: [name]-student

Närhälsan Lidköping Rehabilitation center

Study Description

Brief Summary

Background: Almost half of the Swedish population are overweight or obese. This will probably affect the incidence of osteoarthritis since overweight is a strong risk factor. Osteoarthritis consultations is expected to increase with 30-50% within the next 20 years. Today, in Swedish primary care, both physicians and physiotherapists are primary assessors for patients with suspected knee osteoarthritis. A task shifting with physiotherapists as the only primary assessor could increase the access rate to physicians in primary care for patients with more severe disorders. Yet, it is unclear what effects these different healthcare processes have and the costs of it.

Purpose: The overall purpose of this study is to perform an economic evaluation of two healthcare processes, where a healthcare process initiated by a physiotherapist is compared with when it is initiated with a physician for patients with suspected knee osteoarthritis.

Methods: 100 patients will be randomized either to a physiotherapist or to a physician for first assessment, diagnosis and treatment. Measurements of health-related quality of life and costs for visits to physiotherapist, physician or other healthcare provider, drug prescriptions and sick-leave will be collected. A cost-effectiveness analysis will be conducted, presenting incremental cost-effectiveness ratio (ICER) and a non-parametric bootstrapping will be conducted to demonstrate the uncertainties surrounding the ICER.

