The healthcare process will be started with a physiotherapist assessment and treatment. Treatments could involve individual or group treatment including patient education and physical exercise. Patients can seek a physician anytime after the first assessment with the physiotherapist.

Physician as primary assessor – control

The healthcare process will be started with a physician assessment and treatment. Treatments could involve drug prescription, referral to x-ray, referral to other healthcare providers and sick-leave.

Patients can seek a physiotherapist anytime after the first assessment with the physician.

Outcome Measures

Primary Outcome Measures

Health related quality of life

[Time Frame: Baseline to one year after baseline.]

A Swedish version of Euroqol-5 dimensions-3 levels (EQ5D-3L) was used to assess perceived self-rated HrQoL. EQ5D-index respectively EQ5D-VAS will be presented. The questionnaire contained five dimensions and resulted in an index ranging from -0,549 to 1 using the UK tariffs. An index of 1 indicate full health. The EQ5D-VAS is a visual analogue scale ranging from 0 to 100, where 0 is worst imaginable health state and 100 is best imaginable health state.

Secondary Outcome Measures

A) Costs for physiotherapy contacts

[Time Frame: Baseline to one year after baseline.]

Number of visits registered in patients journal * cost

B) Costs for physician contacts

[Time Frame: Baseline to one year after baseline.]

Number of visits registered in patients journal * cost

C) Costs for sick-leave

[Time Frame: Baseline to one year after baseline.]

Number of sick-leave periods, including number of days with sick leave * costs

D) Costs for drug prescription

[Time Frame: Baseline to one year after baseline.]

Number of drug prescriptions* costs

E) Costs for referral to x-ray

[Time Frame: Baseline to one year after baseline.]

Number of referrals to an x-ray examination of the knee * costs

F) Costs for referral to other healthcare professionals

[Time Frame: Baseline to one year after baseline.]

Number of referrals to other professionals for an examination of the knee * costs

Eligibility Criteria

Ages Eligible for Study: 38 Years and older (Adult, Older Adult)

Sexes Eligible for Study: All

Accepts Healthy Volunteers: No

Inclusion Criteria

- Knee pain most of the days the last month
- Over 38 years old
- Crepitus on active motion
- Morning stiffness less than 30 minutes

Exclusion Criteria

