- Not been diagnosed for current knee pain
- Non-traumatic cause due to current knee pain
- No other rheumatic, severe somatic or psychological diseases that can affect the outcome measures.
- Not pregnant
- Does not know enough Swedish to answer questionnaires.

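### Do the mixed senses in the exclusion list leave the trial population undefined?

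*Combined protocol and SAP*

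**What the plan says.** Under Eligibility Criteria, the Exclusion Criteria list has five items. The first three are "Not been diagnosed for current knee pain", "Non-traumatic cause due to current knee pain" and "No other rheumatic, severe somatic or psychological diseases that can affect the outcome measures". The fourth asks for absence of pregnancy. The fifth is "Does not know enough Swedish to answer questionnaires".

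Other sections describe who was meant to enter:

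- Brief Summary, Methods: "100 patients will be randomized either to a physiotherapist or to a physician for first assessment, diagnosis and treatment".
- Study Design: "Participants with suspected knee osteoarthritis" are the people randomised.
- Eligibility Criteria: "Sexes Eligible for Study: All".
- Primary Outcome Measures: "A Swedish version of Euroqol-5 dimensions-3 levels (EQ5D-3L) was used to assess perceived self-rated HrQoL".

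The section on patient recruitment states that recruitment is complete, and Study Design gives an actual enrolment of 69. No section restates or corrects the list.

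**The concern.** A heading that announces exclusions should be followed by reasons to turn a person away. Here four items state the opposite, and the fifth prevents a simple repair by reading the whole list as requirements. Taken at face value, the list rejects people without a diagnosis, although making the diagnosis is part of what is being compared. It also rejects everyone who is not pregnant, and so every man.

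This list is the document's only statement of who was kept out. If its sense were truly open, a reader could not tell to whom the EQ-5D result and the ICER apply. The trauma item is the most exposed, because trauma is mentioned nowhere else and the item's own phrasing is garbled. What is at stake is the description of the population and how far the result generalises. It is not the validity of the randomised comparison.

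**Working it through.** The plan gives no figure that depends on this list, so the check is mainly one of logic. Take a patient of the kind described elsewhere in the document: no diagnosis yet, non-traumatic pain, no interfering disease, not pregnant, able to answer in Swedish. Apply each item in both senses.

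| Item | Read as an exclusion | Read as a requirement | What settles the sense |
|---|---|---|---|
| 1. Undiagnosed | rejected | accepted | Diagnosis follows randomisation (Brief Summary); osteoarthritis is only suspected (Study Design) |
| 2. Non-traumatic | rejected | accepted | Suspected-osteoarthritis target; same form as items 1, 3 and 4 |
| 3. No interfering disease | rejected | accepted | Its own wording: disease that could disturb the outcome measures |
| 4. No pregnancy | rejected | accepted | All sexes eligible |
| 5. Too little Swedish | accepted | rejected | Self-rated Swedish EQ5D-3L |

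**Count.** The exclusion reading rejects this patient on 4 of 5 items, and the requirement reading on 1 of 5. Neither uniform reading works. The mixed reading (items 1 to 4 as requirements, item 5 as an exclusion) agrees with every other section.

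**Could a reader be misled?** The exclusion reading leaves only pregnant, already diagnosed patients with traumatic knee pain, another interfering disease and adequate Swedish. The requirement reading leaves only people who cannot complete the primary outcome. Nobody would run or interpret a trial on either basis.

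**The trauma item.** The support is indirect but points one way. The item has the same negated form as its neighbours. The target is suspected osteoarthritis, and the Background in the Brief Summary motivates the trial by osteoarthritis linked to overweight. Excluding non-traumatic pain would remove the very patients for whom that argument is made. The inclusion criteria themselves do not mention cause.

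**Does the list enter a design figure?** The Sample size section gives a difference of 0.121, SD 0.2, two-sided 5% significance, 80% power and 14% dropout.

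- Evaluable per group: n = 2 × (1.960 + 0.842)² × 0.2² / 0.121² = 42.9, rounded up to 43.
- With dropout: 43 / (1 − 0.14) = 50.0, the stated 50 per group.

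The figure is reproduced, and rewording the list changes none of its inputs.

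**Could it bias the comparison?** According to the Randomization section, allocation was revealed shortly after the baseline measurement by a coordinator who took no part in screening. Whatever eligibility rule was used therefore applied to both arms alike.

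**The case for a change.** The best case for a change is that an eligibility rule should not have to be rebuilt item by item from other sections. The document was edited for spelling and grammar in 2022, and the list still stands. Correcting it would cost a few words. Finished recruitment makes the correction cheap without making the text right, and a trial meant to inform who should assess these patients first ought to say plainly who they were.

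Part of this stands. The text is wrong as written, and the sense of the trauma item is inferred rather than stated.

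The stronger claim, that the population is misstated and the eligibility of the 69 cannot be verified, does not stand. The four inclusion criteria and the suspected-osteoarthritis target also define the population, and the slip does not touch them. Individual eligibility is checked against screening records in any trial, never against a protocol alone; the Screening procedure section says that those records went to the data collector. The document does not give their content, so it cannot be said from here whether they recorded trauma. Equally, nothing in it suggests that anyone was enrolled wrongly. An eligibility audit prompted by a wording slip would be optional good practice, chiefly for the trauma item.

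**Conclusion.** The observation is correct and the consequence is negligible. Four of five items are worded in the opposite sense to their heading, but the intended list can be recovered from the document: evidently for items 1, 3, 4 and 5, and with fair confidence for item 2.

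This is a clerical slip, and changing the plan would bring no gain. Recruitment was over, so rewording could not admit or remove a single patient. The intention-to-treat analysis, sample size, EQ-5D comparison, costs and ICER would all be the same afterwards. Authors reporting the trial would describe eligibility in the evident sense as a matter of course.

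The conclusion assumes that screening staff applied that evident sense. The document does not reproduce the screening form, but it contains no sign to the contrary. Had they not done so, the description of the population would suffer; the balance between the randomised arms would not.
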